## Visit 01: Randomization/Study Drug Initiation (Day 1-3)

The subject/subject's LAR will have completed the informed consent process during the screening period. The subject must be randomized within 48 hours of initiation of screening procedures and must receive study drug the same calendar day as randomization. Screening and randomization can occur on the same day. Treatment assignment will be by randomization.

The following procedures will be completed, according to Appendix A.

- Collection of interim medical history
- Review inclusion/exclusion criteria to verify continued eligibility
- Review of concomitant medications
- Collection of vital signs (blood pressure, heart rate, respiration rate, temperature)
- Limited physical exam (abdominal, flank, and suprapubic palpation, and examination of any other body site as indicated by subject symptomatology)
- Assessment of cUTI signs and symptoms.

- Ensure pregnancy test (serum or urine) for females of childbearing potential is within 48 hours before initiation of study drug
- Enroll subject in AdvantageEDCSM
- Randomize subject
- Discontinue pre-study therapy. Administer first dose of study drug. Investigator-directed adjustment may be needed as detailed in Figure 1.
- The subject will be directly observed at the time of first dosing by a member of the clinical research team. Provide instructions for its subsequent dosing and storage.
- Dispense memory aid and thermometer and provide instructions for their use
- Collection of AEs grade 2 and above and AESI of any grade occurring after the first dose of study drug
- Review urine culture and blood culture results if available

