3.2.2. Secondary Endpoints

1. The number of solicited and unsolicited adverse events (AEs) grade 2 and above in subjects receiving fosfomycin for the duration of fosfomycin use until 2 days after last dose.
2. The number of serious adverse events (SAEs) in subjects receiving at least two doses of fosfomycin during the trial.
3. The difference in rates and severity of solicited AEs in subjects in Strategy 1 and Strategy 2.
4. The difference in the proportion of subjects achieving treatment success at EOT between Strategy 1 and Strategy 2.

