6.3.4. Safety Population

The Safety Population includes all enrolled subjects who received at least one dose of study drug. The analyses on the Safety Population will be performed using the actual treatment received.

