6.3.5. Fosfomycin Safety Population

The Fosfomycin Safety Population includes all enrolled subjects who received at least two doses of Fosfomycin.

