9.3.1. Solicited Events and Symptoms

Solicited AEs are AEs that are common following administration of these types of antibiotics. The solicited AEs will be collected after first dose of study product is given and until the EOT. If a subject is on fosfomycin, solicited AEs will be collected for 2 days after last dose of fosfomycin or until EOT, whichever occurs later.

Solicited events were recorded for trial Days 1-12, or until study completion or termination, as the maximum severity for each day. Only grade 2 and above solicited AEs will be reported. Target solicited events include insomnia, headache, dizziness, nausea, vomiting, constipation, diarrhea, back pain, rhinitis, pharyngitis, allergic reaction, candidiasis. The solicited events were measured by grading scales as defined in Table 3.

When calculating the incidence of solicited events, each subject will be counted once at the highest severity per day, and any repetitions will be ignored. For summaries presented separately for each treatment group, the denominator will be the number of subjects who received at least one dose of the treatment with non-missing data for the event summarized.

The number and percentage of subjects reporting at least one solicited adverse event of moderate severity or higher will be summarized for each solicited symptom and any symptom in Table 38 for the Safety analysis population. For each event, the denominator is the number of subjects in the applicable treatment group who received at least one dose of study product with non-missing data for the specific event. The 95% CIs calculated using Wilson methodology from a binomial distribution (SAS Proc Freq with a binomial option) will be presented. This analysis will be repeated in Table 39 to include subjects in the Fosfomycin safety analysis population who are those who received at least two doses of Fosfomycin.

For each systemic and any systemic event, the maximum severity over 12 days after the first dose will be summarized. The number and percentage of subjects reporting each event will be summarized by the maximum severity and treatment group. For each event, the denominator is the number of subjects who received the applicable treatment with non-missing data for the specific event. The 95% CI calculated using

Wilson methodology from a binomial distribution (SAS Proc Freq with a binomial option) will be presented [Table 40](#) for the Safety population and [Table 41](#) for the Fosfomycin safety population.

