Notes: N = Number of subjects in the Fosfomycin Safety Population; n = Number of subjects who reported the indicated symptom with moderate severity or higher.

^a 95% CI will be calculated using the Wilson method.

^b 95% CI for the risk difference for strategy 1 compared to strategy 2 will be calculated using the Newcombe method with continuity correction.

^c P-value obtained by Fisher’s Exact Test.

Table 40: Number and Percentage of Subjects Experiencing Solicited Events of Moderate Severity or Higher with 95% Confidence Intervals by Symptom, Study Day Post Dose 1, and Treatment Group - Safety Population

| Symptom | Day 1 | Day 2 | Day 3 | Day 4 | Day 5 | Day 6 | Day 7 | Day 8 | Day 9 | Day 10 | Day 11 | Day 12 | Day 13+ |
|-------------------|---------|---------|---------|---------|---------|---------|---------|---------|---------|---------|---------|---------|---------|
| | n/N (%) | n/N (%) | n/N (%) | n/N (%) | n/N (%) | n/N (%) | n/N (%) | n/N (%) | n/N (%) | n/N (%) | n/N (%) | n/N (%) | n/N (%) |
| Strategy 1 | | | | | | | | | | | | | |
| Any Symptom | x/x (x) | x/x (x) | x/x (x) | x/x (x) | x/x (x) | x/x (x) | x/x (x) | x/x (x) | x/x (x) | x/x (x) | x/x (x) | x/x (x) | x/x (x) |
| Insomnia | | | | | | | | | | | | | |
| Headache | | | | | | | | | | | | | |
| Dizziness | | | | | | | | | | | | | |
| Nausea | | | | | | | | | | | | | |
| Vomiting | | | | | | | | | | | | | |
| Constipation | | | | | | | | | | | | | |
| Diarrhea | | | | | | | | | | | | | |
| Back Pain | | | | | | | | | | | | | |
| Rhinitis | | | | | | | | | | | | | |
| Pharyngitis | | | | | | | | | | | | | |
| Allergic Reaction | | | | | | | | | | | | | |
| Candidiasis | | | | | | | | | | | | | |
| Strategy 2 | | | | | | | | | | | | | |
| Any Symptom | x/x (x) | x/x (x) | x/x (x) | x/x (x) | x/x (x) | x/x (x) | x/x (x) | x/x (x) | x/x (x) | x/x (x) | x/x (x) | x/x (x) | x/x (x) |
| Insomnia | | | | | | | | | | | | | |
| Headache | | | | | | | | | | | | | |
| Dizziness | | | | | | | | | | | | | |
| Nausea | | | | | | | | | | | | | |
| Vomiting | | | | | | | | | | | | | |
| Constipation | | | | | | | | | | | | | |
| Diarrhea | | | | | | | | | | | | | |
| Back Pain | | | | | | | | | | | | | |
| Rhinitis | | | | | | | | | | | | | |
| Pharyngitis | | | | | | | | | | | | | |
| Allergic Reaction | | | | | | | | | | | | | |
| Candidiasis | | | | | | | | | | | | | |

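### SAP Tables 39 and 45 compare Strategy 1 with Strategy 2 inside the Fosfomycin Safety Population, a set formed after randomisation by different routes in the two strategies; they should be descriptive only

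*SAP*

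**What the plan says.** SAP 6.3.5 defines the set: "The Fosfomycin Safety Population includes all enrolled subjects who received at least two doses of Fosfomycin". SAP 9.3.1 takes the solicited-event summary planned for the Safety Population in Table 38 and says: "This analysis will be repeated in Table 39 to include subjects in the Fosfomycin safety analysis population". The text of 9.3.1 mentions only Wilson intervals for that summary. The between-strategy inference is in the table shell, whose footnotes read "95% CI for the risk difference for strategy 1 compared to strategy 2 will be calculated using the Newcombe method with continuity correction" and "P-value obtained by Fisher’s Exact Test".

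For maximum severity, SAP 9.3.1 plans a proportional-odds model with strategy as the covariate, reported in Table 44 (Safety Population) and Table 45 (Fosfomycin Safety Population). The Table 45 shell changes only the population named in the footnote, so it inherits the odds ratio and Wald p-value of Table 44.

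The secondary endpoint that calls for a between-strategy comparison is in SAP 3.2.2: "The difference in rates and severity of solicited AEs in subjects in Strategy 1 and Strategy 2". Protocol 11.4 and SAP 4.5 plan Fisher tests between treatment arms. For fosfomycin recipients both say only that events will be tabulated, from the first fosfomycin dose until 2 days after the last. SAP section 12, which lists changes to the planned analyses, does not mention added tests in this population.

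**The concern.** Membership of the Fosfomycin Safety Population depends on what happens after randomisation, and the route in differs by strategy. SAP 4.1 makes fosfomycin available in Strategy 2 only as an adjustment. The triggers are in-vitro non-susceptibility to levofloxacin, intolerance or allergy, or a condition that raises quinolone risk. Strategy 1 subjects start on fosfomycin and need no trigger. Intolerance can therefore bring a Strategy 2 subject into the set, and it can take a Strategy 1 subject out before the second dose.

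The two columns have both taken fosfomycin, so their difference is not a drug comparison. They are no longer the randomised groups, so it is not a strategy comparison either. A p-value or odds ratio there invites a reader of the clinical study report to attribute to strategy a difference that reflects why subjects switched. Tables 39 and 45 carry no asterisk, so under SAP section 8 they go to the FDA in the abbreviated report. SAP 6.8 tests everything at 5% without multiplicity adjustment, and the low-power caution in SAP section 5 concerns efficacy results only.

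**Working it through.** The plan gives no figure for these tables to reproduce; its power statements concern treatment success.

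**Number of comparisons.** Each table has 12 symptoms plus any symptom, so 13 rows. Tables 39 and 45 give 13 + 13 = 26 p-values. Tables 38 and 44 give another 26, so half of the 52 solicited-event p-values come from the Fosfomycin Safety Population.

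**Event window.** SAP 4.5 counts events for fosfomycin recipients from the first fosfomycin dose to 2 days after the last. Table 39 is described as a repeat of Table 38, and its footnotes do not restate that window. SAP 9.3.1 describes Tables 44 and 45 as covering the follow-up period. An event on levofloxacin before the switch could therefore be counted in the Strategy 2 column.

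**Illustration of the selection effect.** Both drugs are given the same event risk, so the true difference is 0, and pre-switch events are counted. Inputs:
- From the documents: 62 enrolled, 1:1 (SAP 4.1, 4.4.3), taken as 31 per arm; levofloxacin non-susceptibility r = 10-30%, the fluoroquinolone-resistance range in protocol 2.1.
- Assumed, not in the documents: event risk p = 10-20%; share of those with an event who switch s = 0.8; share of Strategy 2 switches that go to fosfomycin f = 0.5; share of Strategy 1 switches before dose 2 e = 0.5.

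Formulas, as a fraction of each arm:
- Strategy 2 in the set with an event: a = p[s + (1 - s)r]f
- Strategy 2 in the set without an event: b = (1 - p)rf
- Strategy 2 event rate = a/(a + b); column size = 31(a + b)
- Strategy 1 event rate = p(1 - se)/(1 - pse)

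Worked case, p = 0.10 and r = 0.20:
- a = 0.10 × (0.8 + 0.2 × 0.2) × 0.5 = 0.042
- b = 0.90 × 0.20 × 0.5 = 0.090
- Column size = 31 × 0.132 = 4.1 subjects; Strategy 2 rate = 0.042/0.132 = 31.8%
- Strategy 1 rate = 0.10 × 0.6/0.96 = 6.25%
- Difference = 6.25 - 31.8 = about -25.6 points

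| p | r | Strategy 2 column | Strategy 2 rate | Strategy 1 rate | Difference (points) | Fisher p ≤ 0.05 |
|---|---|---|---|---|---|---|
| 10% | 10% | 2.7 | 47.7% | 6.2% | -41.4 | 28% |
| 10% | 20% | 4.1 | 31.8% | 6.2% | -25.6 | 23% |
| 10% | 30% | 5.5 | 24.2% | 6.2% | -17.9 | 17% |
| 20% | 10% | 3.8 | 67.2% | 13.0% | -54.2 | 50% |
| 20% | 20% | 5.1 | 51.2% | 13.0% | -38.2 | 37% |
| 20% | 30% | 6.4 | 41.7% | 13.0% | -28.7 | 33% |

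The last column is from 1,500 simulated trials per row. The mean simulated differences ran from about -17 to -55 points.

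Over a wider grid (p = 5-20%, f = 25-100%, e = 0 or 0.5), the Strategy 2 column ranges from 1.1 to 12.8 subjects and the closed-form difference from -8.1 to -54.2 points. These figures show the mechanism and do not forecast this trial.

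**The case against.** The strongest defence is the SAP 4.5 window. If it is applied, an event that began on levofloxacin before the switch is not counted, and the rates in the table above no longer apply. That is right, and it is why the table is only an illustration. It does not make the comparison valid: Strategy 2 members still differ by the reason for their adjustment, and Strategy 1 members who stopped before dose 2 are still missing. No size is claimed for that remainder.

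Reach is also limited. The manuscript table for this population, Table 37, is already one descriptive column, and no decision rule uses the p-values in Tables 39 and 45.

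A reader might infer three stronger things that the documents do not support.
- *That everyone switched for intolerance has a counted event by definition.* The trigger has no grade threshold and is not confined to the 12 listed symptoms. Table 39 counts only grade 2 and above among those 12, so a mild or unlisted reaction can prompt a switch without being counted.
- *That the Strategy 2 column will hold about 3 to 9 subjects* (10-30% of 31). That takes every switch to be to fosfomycin, although three other agents are available, and ignores the two-dose requirement.
- *That SAP 6.3.4 breaks randomisation for the secondary safety endpoint.* It says "The analyses on the Safety Population will be performed using the actual treatment received", and protocol Visit 01 reads "Administer first dose of study drug. Investigator-directed adjustment may be needed as detailed in Figure 1", so a subject adjusted that day might seem to move columns. But SAP 4.4.1 makes the adjustment part of each strategy, the 9.3.1 model is coded by strategy, and Tables 6 and 36 are headed by strategy. Table 6 counts fosfomycin doses under both. The first dose is due on the day of randomisation, so the dosed set should be close to all randomised. The phrase lacks a definition for switchers, and no more than that can be said.

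**Conclusion.** The between-strategy inference in Tables 39 and 45 should not be run. It consists of 26 comparisons in a set defined after randomisation, entered by adjustment in Strategy 2 and by default in Strategy 1, and it goes beyond the tabulation planned in protocol 11.4 and SAP 4.5. This conclusion follows from the definitions alone and needs no assumed rates.

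The size of the bias is not known. If pre-switch events are counted, the illustration gives a spurious difference of tens of points in most scenarios and Fisher rejection in about 17-50% of trials with equal drug risk. It rests on assumed event and switching rates, because the number of switchers is not in the documents. With the SAP 4.5 window the distortion from pre-switch events goes, but the columns remain non-comparable. Tables 38 and 44, which serve the secondary endpoint, are affected only by the missing definition in 6.3.4.

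**What to change.** - Table 39: delete the risk difference, its Newcombe interval and the Fisher p-value. Wilson intervals within each column can stay.
- Table 45: delete the odds ratio, its interval and the Wald p-value. In SAP 9.3.1, confine the proportional-odds comparison to Table 44, and say that the Table 39 repeat is descriptive.
- Keep both tables descriptive, either by strategy as in Table 46 or pooled as in Table 37. Pooling is optional; separate columns preserve the distinction between first-line and post-levofloxacin exposure.
- State in both tables that events are counted from the first fosfomycin dose to 2 days after the last, as SAP 4.5 says.
- Minor clarification in SAP 6.3.4: Tables 38 and 44 compare randomised strategies among subjects who took at least one dose, and adjusted subjects stay in their strategy.

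The cost is a few sentences of SAP text and some table columns. The planned descriptive counts remain, and no valid comparison is lost.

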14.3.1.2 Unsolicited Adverse Events

Table 46: Number and Percentage of Subjects Experiencing Unsolicited Adverse Events with 95% Confidence Intervals by MedDRA System Organ Class and Preferred Term, and Treatment Group - Fosfomycin Safety Population

| MedDRA System Organ Class | MedDRA Preferred Term | Strategy 1 (N=X) | | Strategy 2 (N=X) | |
|---------------------------|-----------------------|---------------------|-------------------------|---------------------|-------------------------|
| | | n | % (95% CI) ^a | n | % (95% CI) ^a |
| Any SOC | Any PT | x | xx (xx, xx) | x | xx (xx, xx) |
| [SOC 1] | Any PT | | | | |
| | [PT 1] | | | | |
| | [PT 2] | | | | |
| [SOC 2] | Any PT | | | | |
| | [PT 1] | | | | |
| | [PT 2] | | | | |

Notes: N = Number of subjects in the Fosfomycin Safety Population. This table presents number and percentage of subjects. A subject is only counted once per PT.

^a 95% CI estimated using Wilson method.

Table 47: Number and Percentage of Subjects Experiencing Unsolicited Adverse Events by MedDRA System Organ Class and Preferred Term, Maximum Severity, Relationship, and Treatment Group – Fosfomycin Safety Population

| MedDRA System Organ Class | MedDRA Preferred Term | Any Incidence | | Severity | | | | | | Relationship to Treatment | | | |
|---------------------------|-----------------------|---------------|----|-----------|----|----------|----|--------|----|---------------------------|----|---------|----|
| | | | | None/Mild | | Moderate | | Severe | | Not Related | | Related | |
| | | n | % | n | % | n | % | n | % | n | % | n | % |
| Strategy 1 (N = X) | | | | | | | | | | | | | |
| Any SOC | Any PT | x | xx | x | xx | x | xx | x | xx | x | xx | x | xx |
| [SOC 1] | Any PT | | | | | | | | | | | | |
| | [PT 1] | | | | | | | | | | | | |
| | [PT 2] | | | | | | | | | | | | |
| [SOC 2] | Any PT | | | | | | | | | | | | |
| | [PT 1] | | | | | | | | | | | | |
| | [PT 2] | | | | | | | | | | | | |
| Strategy 2 (N = X) | | | | | | | | | | | | | |
| Any SOC | Any PT | x | xx | x | xx | x | xx | x | xx | x | xx | x | xx |
| [SOC 1] | Any PT | | | | | | | | | | | | |
| | [PT 1] | | | | | | | | | | | | |
| | [PT 2] | | | | | | | | | | | | |
| [SOC 2] | Any PT | | | | | | | | | | | | |
| | [PT 1] | | | | | | | | | | | | |
| | [PT 2] | | | | | | | | | | | | |

Notes: N = Number of subjects in the Fosfomycin Safety Population. For severity, a subject is counted once per PT and summary according to their highest severity. For relationship, a subject is only counted once per PT and is summarized according to their closest relationship.

Table 48: Number and Percentage of Subjects Experiencing Non-Serious Related Unsolicited Adverse Events by MedDRA System Organ Class and Preferred Term, Maximum Severity, and Treatment Group – Fosfomycin Safety Population

| MedDRA System Organ Class | MedDRA Preferred Term | Any Incidence | | Severity | | | | | |
|---------------------------|-----------------------|---------------|----|-----------|----|----------|----|--------|----|
| | | | | None/Mild | | Moderate | | Severe | |
| | | n | % | n | % | n | % | n | % |
| Strategy 1 (N = X) | | | | | | | | | |
| Any SOC | Any PT | x | xx | x | xx | x | xx | x | xx |
| [SOC 1] | Any PT | | | | | | | | |
| | [PT 1] | | | | | | | | |
| | [PT 2] | | | | | | | | |
| [SOC 2] | Any PT | | | | | | | | |
| | [PT 1] | | | | | | | | |
| | [PT 2] | | | | | | | | |
| Strategy 2 (N = X) | | | | | | | | | |
| Any SOC | Any PT | x | xx | x | xx | x | xx | x | xx |
| [SOC 1] | Any PT | | | | | | | | |
| | [PT 1] | | | | | | | | |
| | [PT 2] | | | | | | | | |
| [SOC 2] | Any PT | | | | | | | | |
| | [PT 1] | | | | | | | | |
| | [PT 2] | | | | | | | | |

Notes: N = Number of subjects in the Fosfomycin Safety Analysis Population. A subject is counted once per PT and is summarized according to their highest severity.

14.3.2 Listing of Deaths, Other Serious and Significant Adverse Events

Table 49: Listing of Serious Adverse Events

[Implementation Note: If the event is ongoing (no stop date), indicate “ongoing” in the “Duration” column. If more than one reason is selected for the reason reported as an SAE, list all reasons in the column, separated by a comma. In the “If Not Related, Alternate Etiology” column, merge the 2 data fields for collecting alternate etiology, separate by a colon. In the CSR, Subject ID should be USUBJID (not PATID) for purposes of de-identification.]

| Adverse Event | Reason Reported as an SAE | Severity | Relationship to Study Treatment | If Not Related, Alternative Etiology | Action Taken with Study Treatment | Subject Discontinued Due to AE | Outcome | MedDRA System Organ Class | MedDRA Preferred Term |
|---|---------------------------|----------|---------------------------------|--------------------------------------|-----------------------------------|--------------------------------|---------|---------------------------|-----------------------|
| Subject ID: , Treatment Strategy: , AE Number: | | | | | | | | | |
| | | | | | | | | | |
| Comments: | | | | | | | | | |
| Subject ID: , Treatment Strategy: , AE Number: | | | | | | | | | |
| | | | | | | | | | |
| Comments: | | | | | | | | | |

Table 50: Listing of Adverse Events of Special Interest

| Adverse Event | Reason Reported as an SAE | Severity | Relationship to Study Treatment | If Not Related, Alternative Etiology | Action Taken with Study Treatment | Subject Discontinued Due to AE | Outcome | MedDRA System Organ Class | MedDRA Preferred Term |
|--|---------------------------|----------|---------------------------------|--------------------------------------|-----------------------------------|--------------------------------|---------|---------------------------|-----------------------|
| Subject ID: , Treatment Group: , AE Number: | | | | | | | | | |
| | | | | | | | | | |
| Comments: | | | | | | | | | |
| Subject ID: , Treatment Group: , AE Number: | | | | | | | | | |
| | | | | | | | | | |
| Comments: | | | | | | | | | |

Tables with similar format

Table 51: Listing of Non-Serious, Unsolicited, Moderate or Severe Adverse Events

14.3.3 Narratives of Deaths, Other Serious and Significant Adverse Events

Not included in SAP, but this is a placeholder for the CSR.

14.3.4 Abnormal Laboratory Value Listings (by Subject)

Not Applicable

14.3.5 Displays of Laboratory Results

Not Applicable.

14.3.6 Displays of Vital Signs

Table 52: Summary of Vital Signs by Visit and Treatment Group

| | | Screening Visit (Visit 00) | | Randomization Visit (Visit 01) | | Interim Visit (Visit 02) | | End-of-Therapy Visit | | Test-of-Cure Visit | |
|---------------------------------|----------|----------------------------|------------|--------------------------------|------------|--------------------------|------------|----------------------|------------|--------------------|------------|
| | | Strategy 1 | Strategy 2 | Strategy 1 | Strategy 2 | Strategy 1 | Strategy 2 | Strategy 1 | Strategy 2 | Strategy 1 | Strategy 2 |
| Temperature (°F) | N | xx | xx | xx | xx | xx | xx | xx | xx | xx | xx |
| | Mean | x.xx | x.xx | x.xx | x.xx | x.xx | x.xx | x.xx | x.xx | x.xx | x.xx |
| | Std | xx.xx | xx.xx | xx.xx | xx.xx | xx.xx | xx.xx | xx.xx | xx.xx | xx.xx | xx.xx |
| | Median | x | x | x | x | x | x | x | x | x | x |
| | Min, Max | xx,xx | xx,xx | xx,xx | xx,xx | xx,xx | xx,xx | xx,xx | xx,xx | xx,xx | xx,xx |
| Diastolic Blood Pressure (mmHg) | N | xx | xx | xx | xx | xx | xx | xx | xx | xx | xx |
| | Mean | x.xx | x.xx | x.xx | x.xx | x.xx | x.xx | x.xx | x.xx | x.xx | x.xx |
| | Std | xx.xx | xx.xx | xx.xx | xx.xx | xx.xx | xx.xx | xx.xx | xx.xx | xx.xx | xx.xx |
| | Median | x | x | x | x | x | x | x | x | x | x |
| | Min, Max | xx,xx | xx,xx | xx,xx | xx,xx | xx,xx | xx,xx | xx,xx | xx,xx | xx,xx | xx,xx |
| Systolic Blood Pressure (mmHg) | N | xx | xx | xx | xx | xx | xx | xx | xx | xx | xx |
| | Mean | x.xx | x.xx | x.xx | x.xx | x.xx | x.xx | x.xx | x.xx | x.xx | x.xx |
| | Std | xx.xx | xx.xx | xx.xx | xx.xx | xx.xx | xx.xx | xx.xx | xx.xx | xx.xx | xx.xx |
| | Median | x | x | x | x | x | x | x | x | x | x |
| | Min, Max | xx,xx | xx,xx | xx,xx | xx,xx | xx,xx | xx,xx | xx,xx | xx,xx | xx,xx | xx,xx |
| Respiratory Rate (breaths/min.) | N | xx | xx | xx | xx | xx | xx | xx | xx | xx | xx |
| | Mean | x.xx | x.xx | x.xx | x.xx | x.xx | x.xx | x.xx | x.xx | x.xx | x.xx |
| | Std | xx.xx | xx.xx | xx.xx | xx.xx | xx.xx | xx.xx | xx.xx | xx.xx | xx.xx | xx.xx |
| | Median | x | x | x | x | x | x | x | x | x | x |
| | Min, Max | xx,xx | xx,xx | xx,xx | xx,xx | xx,xx | xx,xx | xx,xx | xx,xx | xx,xx | xx,xx |

Table 52: Summary of Vital Signs by Visit and Treatment Group *(continued)*

| | | Screening Visit (Visit 00) | | Randomization Visit (Visit 01) | | Interim Visit (Visit 02) | | End-of-Therapy Visit | | Test-of-Cure Visit | |
|--------------------|----------|-------------------------------|------------|-----------------------------------|------------|-----------------------------|------------|----------------------|------------|--------------------|------------|
| | | Strategy 1 | Strategy 2 | Strategy 1 | Strategy 2 | Strategy 1 | Strategy 2 | Strategy 1 | Strategy 2 | Strategy 1 | Strategy 2 |
| Pulse (beats/min.) | N | xx | xx | xx | xx | xx | xx | xx | xx | xx | xx |
| | Mean | x.xx | x.xx | x.xx | x.xx | x.xx | x.xx | x.xx | x.xx | x.xx | x.xx |
| | Std | xx.xx | xx.xx | xx.xx | xx.xx | xx.xx | xx.xx | xx.xx | xx.xx | xx.xx | xx.xx |
| | Median | x | x | x | x | x | x | x | x | x | x |
| | Min, Max | xx,xx | xx,xx | xx,xx | xx,xx | xx,xx | xx,xx | xx,xx | xx,xx | xx,xx | xx,xx |

Note: N = Number of subjects in the Safety Population without missing values for a given parameter at a given visit.

